### **6.7.8. Kansas City Cardiomyopathy Questionnaire**

The KCCQ is a self-administered, 23-item questionnaire developed to provide a better description of health-related QoL in patients with chronic heart failure. The KCCQ assesses physical function, symptoms, social function, self-efficacy, and knowledge, and QoL. At the scheduled time points, this questionnaire should be completed before study drug dosing.

### **6.7.9. EQ-5D Quality of Life**

Quality of life will be assessed through the use of the EQ-5D-5L, a standardized 5 question instrument for use as a measure of health outcomes. At the scheduled time points, This questionnaire should be completed before study drug dosing.

### **6.7.10. Technetium Imaging**

Technetium ( $^{99m}\text{Tc}$ ) imaging by 3D single-photon emission computed tomography (SPECT) will be performed, where possible, depending upon availability of the  $^{99m}\text{Tc}$  imaging tracer.  $^{99m}\text{Tc}$ -Pyrophosphate or DPD can be used as a tracer. The tracer should not be changed for the patient during the study.

Details for the procedure can be found in the Technetium Site Imaging Manual.

### **6.7.11. Fat Pad Aspirates**

At the scheduled time points, two fine-needle aspirate samples of the abdominal fat pad (FNAFP) for amyloid quantification will be collected. Additional timepoints may not be collected depending on the status of the screening aspirate samples. Details on FNAFP collection, processing, and shipment will be in the Study Reference Manual.

## **6.8. Other Assessments**

### **6.8.1. Exploratory Biomarkers and Serology**

At the scheduled time points, aliquots of serum samples will be taken before study drug dosing and frozen to permit testing of the effect of ALN-TTRSC on the expression of exploratory biomarkers (mutant: WT TTR levels, additional cardiac and hepatic-derived proteins that may include galectin-3 and ST2) and serology (ADA).

Mutant and WT TTR will be assessed using a mass spectrometry (MS) method.

Details of how samples will be collected, processed, and stored will be in the Study Laboratory Manual.

Biological samples for biomarker research can be retained on behalf of Alnylam for a maximum of 15 years following the last patient's last visit in the study.

### **6.8.2. Pharmacoconomics Questionnaire**

The burden of disease and healthcare utilization will be assessed using a patient-reported pharmacoconomics questionnaire. At the scheduled time points, this questionnaire should be completed before study drug dosing.

## 7. REPORTING ADVERSE EVENTS

### 7.1. Adverse Event Definition

An AE is any untoward medical occurrence in a patient or clinical investigational patient administered a pharmaceutical product and which does not necessarily have a causal relationship with this treatment.

An AE can therefore be any unfavorable and unintended sign (including an abnormal laboratory finding, for example), symptom, or disease temporally associated with the use of a medicinal product, whether or not considered related to the medicinal product.

Because reductions in TTR and vitamin A are expected responses to ALN-TTRSC, reductions in these parameters will not be considered AEs. While circulating vitamin A levels will be lowered, this is not expected to result in signs or symptoms of severe vitamin A deficiency.

#### 7.1.1. Adverse Events of Clinical Interest

The following events are considered to be AEs of clinical interest:

- ISRs
- Hepatic AEs, including LFT abnormalities considered clinically significant by the Investigator

### 7.2. Serious Adverse Event Definition

An SAE is any untoward medical occurrence that at any dose:

- Results in death;
- Is life-threatening (an event which places the patient at immediate risk of death from the event as it occurred. It does not include an event that had it occurred in a more severe form might have caused death);
- Requires inpatient hospitalization or prolongation of existing hospitalization;
- Results in persistent or significant disability/incapacity;
- Is a congenital anomaly or birth defect;
- An important medical event that may not be immediately life-threatening or result in death or hospitalization but may jeopardize the patient and may require intervention to prevent one of the other outcomes listed above. Examples of such events include allergic bronchospasm requiring intensive treatment in an emergency room or at home, blood dyscrasias, convulsions, or the development of drug dependency or abuse.

### 7.3. Eliciting Adverse Event Information

The patient should be asked about medically relevant changes in his/her health since the last visit. The patient should also be asked if he/she has been hospitalized, had any accidents, used any new medications, or changed concomitant medication routines (both

prescription and OTC). Between clinic visits, the Investigator or designated study site staff should contact the patient by telephone on at least a monthly basis to collect additional information about any medically relevant health changes that may have occurred since the study visit. The patient should also be instructed to contact the study site to report any changes in health status.

In addition to patient observations, AEs will be documented from any clinically relevant laboratory findings, physical examination findings, ECG changes, or other findings that are relevant to patient safety.

#### **7.4. Adverse Event Reporting**

The Investigator is responsible for reporting all AEs that are observed or reported after the first dose of study drug through the Follow-up visit regardless of their relationship to study drug or clinical significance.

Any medical condition that is present when a patient is screened and does not deteriorate is captured as medical history and should not be reported as an AE. However, if it does deteriorate at any time during the study, it should be reported as an AE.

All AEs that occur after the first dose of study drug must be reported in detail on the appropriate CRF page and recorded in the site's source records. The description of the AE will include the onset time and date, duration, severity, seriousness (see Section 7.8) relationship to study drug, action taken, and outcome (including time and date of resolution, if applicable). Adverse events resulting from concurrent illnesses, concomitant medications, or progression of disease states must also be reported. The Medical Dictionary for Regulatory Activities (MedDRA®) will be used to code AEs.

For AEs that are considered AEs of clinical interest, additional clinical information may be collected based upon the severity or nature of the event.

If a patient has ISRs meeting any of the following criteria, the Investigator, or designee, should contact the Medical Monitor and submit a supplemental ISR eCRF:

- ISRs that are recurrent and/or demonstrate a pattern of increasing severity
- Any ISR that is determined to be severe and/or a cause for study drug discontinuation
- Any ISR which, in the opinion of the Investigator, requires further medical evaluation or treatment

In some cases, where it is medically appropriate, further evaluation may include photographs, referral to a dermatologist, skin biopsy, or other laboratory testing. If a biopsy was obtained, the Sponsor may request that the biopsy also be reviewed by a central dermatopathologist. To better understand the safety profile of the study drug, additional analysis of biopsy tissue may be performed as allowed by local regulations.

For patients with hepatic AEs, additional information, including, clinical history, course of event, and local laboratory results to monitor LFT levels or other laboratory parameters, may be collected.

## 7.5. Adverse Event Reporting Period

All AEs that occur after the first dose of study drug must be followed to satisfactory resolution or for a period of 28 days from the last dose of study drug, whichever is the shorter, or the AE is deemed by the Investigator to be chronic or the patient to be stable.

Serious AEs will be followed until resolved or until the SAE is considered by the Investigator to be chronic or the patient to be stable.

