b The End-of-study or ET visit is scheduled approximately 7 days following the last dose. The Follow-up visit is scheduled approximately 4 weeks following the End-of-study or ET visit, if applicable. Patients who discontinue early will be required to report to the clinic for an End of Study visit and a Follow-up visit. For patients who discontinue

early and have provided consent, overall health status will be documented by either telephone contact or non-patient contact follow-up (eg, medical record check) at time points corresponding to study Day 504 (Week 72), if applicable, and study Day 1344 (Week 192).

- c During the treatment period, doses will be administered weekly ( $\pm$  2 days). Doses may be administered at the clinical site or at home according to Section 5.5.
- d Subcutaneous injection of ALN-TTRSC into the abdomen. The upper arm or thigh may also be used (see the ALN-TTRSC Pharmacy Manual).
- e Assessment should be performed before dosing.
- f The pregnancy test will be performed for WOCBP only. A serum pregnancy test should be performed at Screening/Baseline. Urine pregnancy tests at other visits.
- g The serum creatinine values should be in mg/dL to 2 decimal places (e.g., 0.95 mg/dL) OR values in  $\mu$ mol/L to the nearest whole number (e.g., 84  $\mu$ mol/L) when calculating eGFR using the MDRD study equation; see <http://nkdep.nih.gov/lab-evaluation/gfr-calculators.shtml> for an eGFR calculator.
- h Vital sign measurements include blood pressure, pulse rate, oral body temperature, and respiratory rate. Vital signs will be measured manually in the supine position after the patient has rested comfortably for 10 minutes. Each patient's blood pressure should be taken using the same arm. Vital signs should be collected during any unscheduled clinic visit.
- i For the 12-Lead ECG, each lead shall be recorded for at least 3 beats at a speed of 25 mm/s. Triplicate recordings will be obtained. The electrophysiologic parameters assessed will be rhythm, ventricular rate, PR interval, QRS duration, QT interval, ST and T-waves and QTcB.
- j Coagulation studies include PT, aPTT, and INR and will be performed on all patients.
- k Blood samples for vitamin A will be analyzed by a central laboratory.
- l Refer to Table 4 for PK Sampling Schedule.

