#### **4.4.2. Handling of Withdrawals**

In the event a patient withdraws or is withdrawn from the study, the Investigator will inform the Medical Monitor at the clinical research organization (CRO) and Alnylam immediately. If there is a medical reason for withdrawal, the patient will remain under the supervision of the Investigator for protocol-specified safety follow up procedures.

When a patient withdraws or is withdrawn from the study, every effort should be made to conduct a complete ET visit as soon as possible following the patient's withdrawal, as described in Table 2.

If a patient is withdrawn for an AE, appropriate medical care should be provided and, if possible, the AE should be followed until resolution.

A patient who fails to return for final evaluations will be contacted by the site in an attempt to have the patient comply with the protocol. The site will follow up by telephone at least twice and send a registered letter to any patient who fails to return for the final evaluation.

When a patient withdraws from the study, the primary reason for discontinuation must be recorded in the appropriate section of the case report form (CRF) and all efforts will be made to complete and report the observations as thoroughly as possible.

For patients who discontinue early and have provided consent, overall health status will be documented by telephone contact or non-patient contact follow-up (eg, medical record check) at the scheduled time points.

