**Urine Pregnancy Testing (WOCBP only)**

---

- $\beta$ -human chorionic gonadotropin

---

Additional and repeat testing may be performed at the discretion of the Investigator.

In the event of an unexplained clinically relevant abnormal laboratory test occurring after study drug administration, the test should be repeated and followed up at the discretion of the Investigator until it has returned to the normal range or stabilized, and/or a diagnosis is made to adequately explain the abnormality.

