#### **6.4.9. Adverse Events**

Adverse events will be collected beginning with the first dose of study drug and through the Follow-up visit. After Day 84, the site should contact the patient by phone at least monthly to collect information on adverse events between clinic visits. See Section 7 for more details on the collection and reporting of AEs.

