## 7.7. Assessment of Severity

The severity of each AE is to be classified as mild, moderate, severe, or life threatening according to the following criteria:

**Mild:** Mild events are those which require minimal or no treatment and do not interfere with the patient's daily activities.

**Moderate:** Moderate events are those which cause sufficient discomfort to interfere with normal everyday activities and may require minor analgesics or antiemetics.

**Severe:** Severe events are those which interrupt a patient's usual daily activity and may require systemic drug therapy or other therapy.

**Life Threatening:** Life threatening events put the patient's life at risk.

Changes in severity should be documented in the medical record to allow assessment of the duration of the event at each level of severity. Adverse events characterized as intermittent require documentation of the start and stop of each incidence. When changes in the severity of an AE occur more frequently than once a day, the maximum severity for the experience that day should be noted. If the severity category changes over a number of days, then those changes should be recorded separately (with distinct onset dates).

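### Does the 28-day limit on following non-serious adverse events clash with collecting them through a later Follow-up visit?

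*Protocol*

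**What the plan says.** Four parts of the protocol bear on how long an AE is tracked.

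- **Follow-up of known events, Section 7.5.** AEs "must be followed to satisfactory resolution or for a period of 28 days from the last dose of study drug, whichever is the shorter", or until the investigator judges the event chronic or the patient stable. A separate sentence gives serious AEs a rule with no day limit.
- **Collection and reporting, Sections 6.4.9 and 7.4.** "Adverse events will be collected beginning with the first dose of study drug and through the Follow-up visit". The investigator reports "all AEs that are observed or reported after the first dose of study drug through the Follow-up visit". The record includes the "outcome (including time and date of resolution, if applicable)".
- **Timing of the last visits, Table 2 footnote b (repeated in the introduction to Section 6).** The End-of-study or early termination (ET) visit is "approximately 7 days following the last dose. The Follow-up visit is scheduled approximately 4 weeks following the End-of-study or ET visit". Patients who stop early must attend both visits.
- **Special cases.** Section 4.4.2: "If a patient is withdrawn for an AE, appropriate medical care should be provided and, if possible, the AE should be followed until resolution". For an unexplained, clinically relevant abnormal laboratory result, Section 6.4.5 says "the test should be repeated and followed up at the discretion of the Investigator until it has returned to the normal range or stabilized"; finding an explanatory diagnosis is a further stopping point there.

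Section 7.7 adds that severity changes go into the medical record "to allow assessment of the duration of the event at each level of severity".

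**The concern.** The 28 days in Section 7.5 run from the last dose, whereas the 28 days in the visit schedule run from the End-of-study visit. The two clocks are a week apart. On the nominal calendar, an AE that starts in the last week before the Follow-up visit must be reported with an outcome, although its required follow-up expired before it began. A non-serious AE that causes withdrawal comes under both Section 7.5 (the shorter of resolution or 28 days) and Section 4.4.2 (to resolution, if possible), and no passage says which governs. The heading of Section 7.5 refers to a reporting period, which could lead a site to treat 28 days as the end of reporting.

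If sites read this differently, the last recorded status of an open event could be as of Day 1365, the Follow-up visit or resolution. Safety and tolerability are the primary objective and only about 25 patients are planned, so uneven AE records would deserve attention if they reached the analysis.

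**Working it through.** **Inputs.** Last dose about Day 1337 (Section 5.5); End of study Day 1344 and Follow-up Day 1372 with a window of ±14 days (Table 2); follow-up limit 28 days from the last dose (Section 7.5).

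**Day arithmetic.**

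- Last dose to End of study: 1344 − 1337 = 7 days.
- End of study to Follow-up: 1372 − 1344 = 28 days.
- Last dose to Follow-up: 1372 − 1337 = 35 days.
- End of the Section 7.5 limit: 1337 + 28 = Day 1365.
- Nominal gap: 1372 − 1365 = 7 days.
- With the visit window: Follow-up on Days 1358 to 1386, which is 21 to 49 days after Day 1337. The gap runs from 0 (visit at 21 to 28 days) to 49 − 28 = 21 days.

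So 28 days matches the interval between the last two visits, not the interval from the last dose.

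**Can a site obey all the passages at once?**

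1. *Section 7.5 with 6.4.9 and 7.4.* The latter two fix when an event counts as reportable. Section 7.5 fixes how long a known event must be pursued, and nothing in it forbids recording a later outcome. Section 7.4 asks for a resolution date only where there is one, so an event that starts on Days 1366 to 1372 can be reported with its status at that time.
2. *Section 7.5 with 4.4.2.* The first is a requirement; the second is a softer, more specific request qualified by feasibility. Following an event beyond 28 days breaches neither.
3. *Section 7.5 with 6.4.5.* The latter concerns repeat testing of laboratory abnormalities and leaves it to the investigator's discretion. It is not a rule on when AE outcome recording closes.

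**Would an open event be lost?** No visit is scheduled on Day 1365. The next contact in the schedule after Day 1344 is the Follow-up visit. Table 2 shows AE review as continuous, and Section 7.3 has staff ask about health changes since the previous visit. An event open at 28 days would ordinarily be asked about and updated there.

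**Which planned outputs depend on the difference?** Sections 8.2 and 8.2.3 tabulate all treatment-emergent AEs, related AEs, serious AEs, discontinuations due to AEs, and AEs by severity.

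- Incidence and relatedness rest on events reported through the Follow-up visit under Section 7.4.
- Serious AEs have their own follow-up rule.
- A discontinuation due to an AE is settled when dosing stops, before the post-dose period begins.
- A change in severity lasting over days is recorded separately with its own onset date (Section 7.7), so worsening before the Follow-up visit is reportable in its own right.

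None of these tabulations uses AE duration or resolution date.

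**The case for a change.** The strongest case for a change rests on AEs that cause withdrawal. The protocol itself reports that injection site reactions were occasionally prolonged and sometimes led to discontinuation (Sections 1.3 and 1.6.1), and that transaminase elevations led to interruption or discontinuation in some subjects (Section 1.6.2). These are the two AEs of clinical interest in Section 7.1.1. Persistent, non-serious events that end treatment are therefore plausible here, and for them Sections 7.5 and 4.4.2 do differ. The Follow-up visit includes liver tests, so an abnormality can first appear after the 28-day limit has nominally passed. This is also an instruction to sites, which a statistical analysis plan cannot correct, and rewording it would cost little.

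Part of this stands. The clocks do not match, no order of precedence is stated, and resolution dates of some long-lasting non-serious AEs could be recorded to different end dates. But a site that follows such an event to resolution meets both passages. A site that stops at 28 days has still reported the event, its severity, its relationship to drug and the discontinuation. Recording status at the Follow-up visit, the obvious remedy, is largely what the schedule already brings about.

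**Conclusion.** The wording is inconsistent, but the plan needs no change on this account. The mismatch is nominally 7 days, and 0 to 21 days across the visit window. It touches only the outcome or resolution date of non-serious AEs still open more than 28 days after the last dose. Serious AEs, AE incidence and all tabulations in Sections 8.2 and 8.2.3 stay the same under either reading.

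This rests on three assumptions. Sites review open events at the Follow-up visit, as Sections 6.4.9 and 7.3 and Table 2 imply. The visit is held near its nominal day; after early termination the interval from the last dose can differ, because Section 4.4.2 times the ET visit from withdrawal. And no analysis of AE duration is added; if one were, events open at last contact could be reported as unresolved at that date. The protocol gives no AE rates for the post-dose period, so the number of affected events cannot be estimated. How long an event should be followed clinically is for the sponsor to decide and is not judged here.

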## 7.6. Assessment of Causality

Causal relationship assessment to drug treatments is required for purposes of reporting AEs. To promote consistency, the following guidelines should be taken into consideration along with good clinical and scientific judgment when determining the relationship of drug treatments to an AE:

**Definitely Related:** A clinical event, including laboratory test abnormality, occurring in a plausible time relationship to the medication administration, and which cannot be explained by concurrent disease or other drugs or chemicals. The response to withdrawal of the drug should be clinically plausible.

**Possibly Related:** A clinical event, including laboratory test abnormality, with a reasonable time sequence to the medication administration, but which could also be explained by concurrent disease or other drugs or chemicals. Information on the drug withdrawal may be lacking or unclear.

**Unlikely Related:** A clinical event, including laboratory test abnormality, with little or no temporal relationship to medication administration, and which other drugs, chemicals, or underlying disease provide plausible explanations.

**Not Related:** A clinical event, including laboratory test abnormality, that has no temporal relationship to the medication or has more likely alternative etiology.

## 7.7. Assessment of Severity

The severity of each AE is to be classified as mild, moderate, severe, or life threatening according to the following criteria:

**Mild:** Mild events are those which require minimal or no treatment and do not interfere with the patient's daily activities.

**Moderate:** Moderate events are those which cause sufficient discomfort to interfere with normal everyday activities and may require minor analgesics or antiemetics.

**Severe:** Severe events are those which interrupt a patient's usual daily activity and may require systemic drug therapy or other therapy.

**Life Threatening:** Life threatening events put the patient's life at risk.

Changes in severity should be documented in the medical record to allow assessment of the duration of the event at each level of severity. Adverse events characterized as intermittent require documentation of the start and stop of each incidence. When changes in the severity of an AE occur more frequently than once a day, the maximum severity for the experience that day should be noted. If the severity category changes over a number of days, then those changes should be recorded separately (with distinct onset dates).

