### 1.3. Summary of Clinical Data with ALN-TTRSC

Study ALN-TTRSC-001 was a Phase 1 randomized, double-blind, placebo-controlled, study ALN-TTRSC administration in healthy subjects. Subjects received single ascending doses or multiple ascending doses of up to 10 mg/kg or fixed doses of 500 or 600 mg ALN-TTRSC or placebo. In the multiple-dose cohorts, subjects received a total of 10 doses over a 35 day period administered as 5 daily SC doses followed by 5 weekly doses.

In this study, ALN-TTRSC was generally well-tolerated. The majority of treatment-emergent adverse events (AEs) were mild or moderate in severity and considered unrelated to study treatment. There were no serious adverse events (SAEs). Injection site reactions (ISRs) were the most common AEs related to study treatment. All ISRs were mild or moderate in severity and resolved without sequelae. Overall, the incidence of alanine transaminase (ALT) and aspartate transaminase (AST) elevation  $>1\times$  upper limit of normal (ULN) was similar in placebo and ALN-TTRSC-treated subjects. One subject who received 600 mg ALN-TTRSC developed an asymptomatic elevation of ALT (4.3 $\times$ ULN) and AST (1.9 $\times$ ULN), which was defined in the protocol as a dose-limiting toxicity and resulted in study discontinuation. There were no other AEs leading to dose interruption or dose reduction. No elevations in cytokines, C-reactive protein, or other abnormal clinical findings were noted. The pharmacodynamic (PD) effect of ALN-TTRSC was dose-dependent and resulted in  $> 85\%$  reduction of TTR at  $\geq 5$  mg/kg of ALN-TTRSC and was accompanied by reduction of RBP and vitamin A. Fixed doses of 500 mg and 600 mg ALN-TTRSC also demonstrated similar safety and PD effect over a wide range of body weights compared to that observed in cohorts with weight-based dosing.

Patients completing Study ALN-TTRSC-002 are eligible to enroll into the Phase 2, open label, extension study (ALN-TTRSC-003) designed to evaluate the safety and tolerability of long-term ALN-TTRSC dosing; additional information will be evaluated

including PK, PD, and clinical activity. Patients will receive 500 mg ALN-TTRSC weekly for approximately 4 years.

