## **5.5. Dose, Route, and Schedule of Study Drug Measurement of Patient Compliance**

Patients meeting the eligibility criteria will initially receive a daily SC dose of 500 mg of ALN-TTRSC over 5 consecutive days (Days 0, 1, 2, 3, and 4). Doses should be administered 24 ±4 hours apart.

Patients will then receive the same dose of ALN-TTRSC on Day 7 and then weekly from Day 14 through approximately Day1337 (or ET). The Day 7 dose should be administered within ±1 day of the planned dosing date. The weekly doses starting on Day 14 should be administered within ±2 days of the planned dosing date.

Study drug injection during clinic visits will be administered by qualified site staff under the supervision of the Investigator or designee. Dosing after Day 7 may be administered at home by a healthcare professional trained in the protocol, or at the clinic if dosing coincides with the clinic visit for other assessments. The preferred site of injection is the abdomen. Optional additional sites are the upper arms and thighs. The site of injection will be rotated. If a local reaction around the injection site occurs, photographs may be taken.

At the discretion of the Investigator, after the Day 84 dosing visit, and if the patient has not experienced any severe or serious AEs considered related to the study drug within the previous 12 weeks, patients/caregivers may be trained by the Investigator or qualified site staff in the administration of the study drug, according to the protocol dosing requirements. Training of the patient/caregiver in study dosing should be recorded in the site source documentation.

Detailed instructions can be found in the Pharmacy Manual.

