## **5.6. Criteria for Dose Interruption, Dose Modification, or Discontinuation of Study Drug**

During the study, if a patient has an elevation of AST, ALT, or total bilirubin (unless due to Gilbert's Syndrome)  $>3 \times \text{ULN}$ , repeat assessments of AST, ALT, and total bilirubin should be performed within 72 hours. The patient should be followed closely, with LFT assessments performed weekly, and as medically indicated to guide patient management. Close monitoring may be discontinued when ALT, AST, and total bilirubin return to  $\leq 3 \times \text{ULN}$ . Additional, and repeat assessments, may be performed at the discretion of the Investigator.

- Dosing will be held for the following liver function test abnormalities: AST or ALT elevation of  $\geq 3 \times \text{ULN}$  in association with either total bilirubin elevation of  $\geq 1.5 \times \text{ULN}$  or gastrointestinal symptoms including nausea, vomiting and/or abdominal pain;
- AST or ALT elevation  $\geq 5 \times \text{ULN}$

Under these circumstances, the Medical Monitor and Investigator will decide on the appropriate action regarding frequency of repeat liver function tests and resumption of dosing.

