#### 8.2.3. Safety Analyses

Adverse events will be summarized by MedDRA® system organ class and preferred term. Separate tabulations will be produced for all TEAEs, treatment-related AEs (those considered by the Investigator as at least possibly drug related), SAEs, discontinuations due to AEs, and AEs of various grading severity.

Descriptive statistics will be provided for clinical laboratory data and vital signs data, presented as both actual values and changes from baseline relative to each on-study evaluation and to the last evaluation on study.

Descriptive statistics will be provided for ECG interval data and presented as both actual values and changes from baseline relative to each on-study evaluation and to the last evaluation on study. Details of any abnormalities will be included in patient listings.

Details of any abnormalities will be included in patient listings.

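### The Mild, Moderate and Severe definitions in Section 7.7 have no laboratory criterion, so a symptom-free transaminase rise that holds dosing under Section 5.6 is graded Mild

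*Protocol*

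**What the plan says.** Section 7.7 of the protocol sets a single scale for all events: "The severity of each AE is to be classified as mild, moderate, severe, or life threatening according to the following criteria". The lowest grade is "Mild events are those which require minimal or no treatment and do not interfere with" daily activities. Moderate needs discomfort that disturbs everyday activity, Severe needs an interruption of usual activity, and Life Threatening needs a risk to life. No laboratory threshold and no external grading scale appears in this section or elsewhere in the protocol.

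Laboratory findings are nevertheless in scope as AEs. Section 7.1 counts an abnormal laboratory result as a possible AE, Section 7.3 has AEs documented from relevant laboratory findings, and every causality category in Section 7.6 names laboratory abnormalities. One of only two AEs of clinical interest in Section 7.1.1 is "Hepatic AEs, including LFT abnormalities considered clinically significant by the Investigator".

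Section 5.6 states "Dosing will be held for the following liver function test abnormalities" and includes any AST or ALT of at least 5 x ULN, with no symptom needed. Section 8.2.3 plans separate tables for "SAEs, discontinuations due to AEs, and AEs of various grading severity". Section 5.5 allows training in self-administration after Day 84, at the Investigator's discretion, "if the patient has not experienced any severe or serious AEs considered related to the study drug within the previous 12 weeks".

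**The concern.** Safety and tolerability is the primary objective, and AEs by severity are a named output. The hepatic risk described in Section 1.6.2 consists mostly of enzyme rises without symptoms. A scale built on how the patient feels and functions cannot rank such events by size. Those large enough to hold dosing would then be tabulated alongside trivial ones, and a reader of the severity tables could not tell them apart.

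The grade is also used elsewhere. It feeds the word severe in the Section 5.5 condition. Section 7.4 also lets the extra information collected on AEs of clinical interest depend on the severity or nature of the event. The Investigator assigns the grade at the site during the trial, so a later analysis plan can add laboratory tables beside it but does not change it.

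**Working it through.** The plan gives no figure to reproduce on this point. The check applies the Section 7.7 definitions to one defined event and follows the resulting grade through the protocol.

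**Event:** ALT at or above 5 x ULN, no symptoms, no treatment given, usual activities unchanged, reported as an AE.

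| Grade in 7.7 | What it requires | Does the event meet it? |
|---|---|---|
| Mild | Minimal or no treatment; no interference with activities | Yes |
| Moderate | Discomfort that interferes with everyday activities | No, there is no discomfort |
| Severe | Interruption of usual daily activity | No, activity is unchanged |
| Life Threatening | Risk to life | Only if the Investigator judges so |

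The literal grade is therefore Mild. Two things could remove it from Mild. The first is a judgement that life is at risk. The second is a need for more than minimal treatment; without discomfort or lost activity, such an event would still not match Moderate or Severe.

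**The same event elsewhere in the protocol:**

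- *Section 5.6:* dosing is held, on the enzyme value alone.
- *Section 1.6.2:* mild describes rises below 3 x ULN. Higher rises are set apart as those that led to interruption or discontinuation. The protocol thus describes liver findings by magnitude but gives sites a scale without it.
- *Section 7.1.1:* the event is of clinical interest if it is a hepatic AE. For an LFT abnormality, the text turns on the Investigator's view of clinical significance and does not refer to the Section 5.6 thresholds.
- *Section 8.2.3:* the event is counted in the lowest row of the severity tables.
- *Section 5.5:* the event does not count as severe. It counts towards the condition only if judged serious and related.

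**Illustration of scale.** Section 8.1 plans approximately 25 patients. One patient placed in a different severity row moves that row by 1/25 = 4 percentage points. The protocol gives no count of symptom-free rises at or above 5 x ULN, so this shows what one patient weighs and is not an estimate of how many are affected.

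**The case against.** The strongest reply is that a functional severity scale with separate laboratory reporting is a legitimate design choice. Section 8.2.3 summarises laboratory values and their changes and lists abnormalities. Section 7.4 records the action taken for each AE, so a dose hold is captured whatever the grade. Discontinuations due to AEs have their own table. Laboratory toxicity-grade tables commonly sit in the SAP, which is not shown. This stands as a limit on the harm: the information is recorded and can be recovered. It does not answer the narrower point that Section 7.7 applies its scale to each AE, laboratory events included, and that the tables built on that scale put dose-hold events in the lowest row.

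Several stronger readings are tempting, and the protocol does not support them.

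- *A rise of any size is Mild.* Life Threatening rests on risk to life, and Mild excludes events that need more than minimal treatment.
- *The self-administration condition is defeated.* Section 5.5 also covers serious events and leaves the decision to the Investigator. The important-medical-event criterion in Section 7.2 does not depend on the severity grade, and Section 7.8 applies seriousness to laboratory abnormalities expressly. Resumption after a hold is a separate decision of the Medical Monitor and Investigator. Only the severe part of the condition is weakened.
- *The grade lengthens the interval between scheduled LFTs.* That schedule is the same whatever the grade and whoever injects, and Section 5.6 adds weekly tests while values stay above 3 x ULN.
- *The Phase 1 case of ALT 4.3 x ULN in Section 1.3 is a dose-hold example.* It was symptom-free and "which was defined in the protocol as a dose-limiting toxicity and resulted in study discontinuation", but under another study's rule. That value alone is below the 5 x ULN hold here.
- *The summary that most AEs were mild or moderate is a product of this scale.* Sections 1.3 and 1.6.2 describe enzyme rises separately by ULN multiple, and the severity scales of the other studies are not given.

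**Conclusion.** The point holds in a limited form. Mild, Moderate and Severe in Section 7.7 contain no laboratory criterion, so a symptom-free, untreated AST or ALT rise at or above 5 x ULN meets Mild while Section 5.6 holds dosing for it. This is at odds with the magnitude-based use of mild in Section 1.6.2, and it understates a named AE of clinical interest in the severity tables for the primary objective.

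The conclusion assumes that sites apply Section 7.7 as written, that the abnormality is reported as an AE, and that it is not judged a risk to life. How many patients are affected cannot be derived from the protocol. Because laboratory summaries and action taken preserve the underlying data, this is a worthwhile, inexpensive correction to reporting. It does not show that safety events go unrecorded or that the self-administration condition fails.

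**What to change.** 1. In Section 7.7, grade laboratory-based AEs by magnitude with a named, published laboratory toxicity scale. Keep the present wording for symptomatic events.
2. Regrade hepatic AEs already reported from the LFT values on file, so that one scale applies throughout the severity tables.
3. In Section 7.1.1, count any LFT result that meets a Section 5.6 threshold as a hepatic event of clinical interest, without a further judgement of clinical significance.
4. Reconcile Sections 7.7, 5.6 and 1.6.2 with the severe part of the Section 5.5 condition, so that it is clear how a dose-hold liver event counts there. Which clinical rule applies is for the sponsor to decide.

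The cost is protocol and CRF-completion wording plus a one-time regrading; no new data are needed. The downside is that some hepatic events will be reported at a higher grade than under the present text, and this should be explained where results are compared with earlier summaries.
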